6. STUDY TREATMENT

6.1. Clinical Supplies

6.1.1. Aldafermin

Aldafermin is formulated in aqueous isosmotic buffer solution with 0.01% polysorbate-20. It is filled into 1-mL type I glass syringes, with a 29-g staked needle, needle shield, grey rubber plunger, and plastic plunger rod. Filled syringes are labeled and packaged into trays and cardboard cartons.

Aldafermin is provided as a sterile solution for injection in a single use prefilled syringe for SC administration at doses of 0.3 mg, 1 mg, and 3 mg (note: under protocol Version 5.0 and subsequent versions, randomization to the 0.3 mg aldafermin dose was discontinued). The drug product is manufactured for NGM under current Good Manufacturing Practice (cGMP) regulations [REDACTED]
[REDACTED], a contract manufacturing facility that has undergone FDA inspection.

6.1.2. Aldafermin-matched Placebo

Aldafermin placebo is formulated in aqueous isosmotic buffer solution with 0.01% polysorbate-20. It is filled into 1-mL type I glass syringes, with a 29-g staked needle, needle shield, grey rubber plunger, and plastic plunger rod. Filled syringes are labeled and packaged into trays and cardboard cartons.

Aldafermin placebo is provided as a sterile solution for injection in a single use- pre-filled syringe for SC administration. The drug product is manufactured for NGM under cGMP regulations [REDACTED]
[REDACTED], an FDA-inspected contract manufacturing facility.

6.1.3. Rosuvastatin / Placebo

Commercial rosuvastatin tablets will be over-encapsulated and will be supplied as 5 mg, 10 mg, 20 mg, or 40 mg strengths in multi-count bottles. Inactive ingredient microcrystalline cellulose will be used to backfill over-encapsulated rosuvastatin calcium tablets.

Placebo capsules for rosuvastatin calcium contains only microcrystalline cellulose and will be supplied in multi-count bottles. The capsules used for the active and placebo are opaque, Swedish Orange, size A, hard gelatin capsules containing gelatin, titanium oxide, and FDA/E172 red iron oxide. Refer to [Appendix 5](#) for the rosuvastatin package inserts.

6.1.3.1. Rosuvastatin Supply

Upon subject consent, over-encapsulated rosuvastatin/placebo bottles will be delivered to his/her designated location (e.g., home, office) via a courier service vendor. Delivery can be done through either a depot or central pharmacy. In compliance with data privacy regulations, the vendor has a data privacy system in place to cover any local obligations. If subjects do not agree to use this courier service, they have the option to pick up the rosuvastatin/placebo bottles at the study site.

6.2. Preparation / Handling / Storage / Accountability

6.2.1. Preparation

6.2.1.1. Aldafermin

Subjects will be instructed to self-administer aldafermin/placebo at relatively the same time each day. Study drug/placebo syringes will be equilibrated to room temperature prior to use and will be administered as a SC injection in the abdomen. On Day 1, subjects will be trained on self-administering a SC injection. During the treatment visits, self-administration will occur in the clinic under observation by clinic staff. Re-training will be provided as required. Written dose preparation and administration instructions will be provided to subjects. Subjects will be required to complete a daily study drug/placebo administration diary.

6.2.1.2. Rosuvastatin / Placebo

Subjects will be instructed to take one capsule of rosuvastatin/placebo once a day by mouth at approximately the same time each day. All bottles will be blinded. The subject will be contacted by the site a few days after study visits and instructed as to which bottle to dose from. During the on-treatment visits, subjects will take their study drug to clinic visits and dose from the dosing bottle dispensed at the last visit in the clinic under observation by clinic staff. The subject will be required to complete a daily study drug/placebo dosing diary.

6.2.2. Storage

Aldafermin/placebo syringes are to be stored at the clinical site in the provided packaging and refrigerated at 2°C–8°C (36°F–46°F) in a secure, controlled access- location protected from light. At the subject's home, aldafermin/placebo syringes are to be stored in the provided packaging and refrigerated at 2°C–8°C (36°F–46°F) in a location protected from light (e.g., refrigerator).

Rosuvastatin /placebo bottles should be stored at room temperature, at 68°F–77°F (20°C–25°C) and in a dry place.

Subjects will be instructed to keep both study drugs out of the reach of children and other family members who may have access to the storage location.

6.2.3. Accountability

The principal investigator (PI) is responsible for ensuring that a current record of inventory/drug accountability (aldafermin/placebo and rosuvastatin/placebo) is maintained. Inventory records must be readily available for inspection by the study monitor and are open to inspection by regulatory authorities at any time.

Upon receipt of the investigational drug/placebo, the designated site personnel will visually inspect the shipment, verify the number and condition of study drug received, and confirm receipt of study drug.

At the completion of the study, all unused study drug supplies will be returned to the sponsor (or designee) or disposed of by the clinic, per the sponsor's (or designee's) written instructions.

6.3. Randomization and Blinding

Subjects will be randomized to a treatment group using [REDACTED] [REDACTED]. Treatment assignment will be blinded to the sites, study subjects, sponsor study team, and sponsor Medical Monitor throughout the study period.

Rosuvastatin and matched placebo will be over-encapsulated to maintain the blind at the sites and with the sponsor study teams. Initiation and ongoing dose adjustments of rosuvastatin/matched placebo will be managed through the [REDACTED] [REDACTED] but blinded to the treatment assignment (aldafermin or matched placebo). The sponsor and study sites will be blinded to LDL-C values and the specific rosuvastatin dosing decisions.

6.3.1. Removal of Study Blind (if applicable)

Breaking of any blind will be available to the PI [REDACTED] The subject's treatment assignment will be available to the PI in the event of a medical emergency or an AE that necessitates identification of the study drug for the welfare of that subject. Except in the case of a medical emergency, the PI and clinic staff will remain blinded during the conduct of the study and until such time that all discrepancies in the clinical database are resolved (i.e., at the time of the database lock). The date and time when the PI removed the study blind for an individual subject will be documented by [REDACTED] [REDACTED] to the sponsor.

6.4. Concomitant Medications

Any medication taken at least once within 90 days prior to Screening Visit and during the study period as well as the reason for use will be recorded in the source documents and the CRFs. Subjects should refrain from the use of any new prescription medications or products or changes in the dose or frequency of existing therapies from Screening to Day 1 until EOS.

The sponsor Medical Monitor or designee should be informed of any changes or addition of prohibited medications during this time.

6.4.1. Prohibited Medications:

- Investigational agents, other than aldafermin, or devices for any indication, within 28 days or 5 half-lives of the drug (whichever is longer) prior to Screening through the end of the study.
- Non-statin lipid lowering agents, from Day 1 of Screening through the end of the study
 - Example medications to avoid include: Cholestyramine, colesevelam, PCSK9 inhibitors (evolocumab or alirocumab), colestid, fibrates, fenofibrates, pharmacologic (dose of >1 g daily) fish oil
- Statins other than the study provided rosuvastatin from Week 2 through the end of the study:
 - Prior statin use must be at a reasonably stable dose for 3 months prior to Screening and will continue as a concomitant medication until Week 2.

- Agents used for the treatment of any condition listed in the exclusionary enrollment criteria (see [Section 5.1](#)).
- Weight loss medications including orlistat, phentermine, qsymia, lorcaserin hydrochloride, naltrexone hydrochloride, benzphetamine, diethylpropion, phendimetrazine, from 3 months prior to Screening through the end of the study.
- Contraindicated medications according to the rosuvastatin package insert ([Appendix 5](#)), including; cyclosporine, gemfibrozil, protease inhibitors (atazanavir, ritonavir, lopinavir, simeprevir), coumarin anticoagulants, fenofibrates, niacin, colchicine, from randomization through the end of the study.
- Known hepatotoxic agents (refer to [Appendix 6](#)).
- Anabolic steroids.

This list of prohibited medications along with [Appendix 6](#), are not an inclusive list. investigator judgement must be used to avoid prohibited medications and to justify initiating any other medication during the study.

6.4.2. Restricted Concomitant Medications / Treatments:

- Statin Therapies:

For statin experienced subjects only, the following daily dose of approved statin therapies will allow for enrollment consideration if dosing is stable at least 3 months with reasonable dose adjustment (as per Medical Monitor's judgment) prior to Screening through Week 2. All subjects will transition to study rosuvastatin treatment at Week 2 according to the protocol. From Week 2 onward, over-encapsulated rosuvastatin or matched placebo will be dispensed according to the Lipid Lowering Algorithm ([Appendix 4](#)).

- Atorvastatin: ≤ 40 mg/day
- Fluvastatin: ≤ 40 mg/day
- Lovastatin: ≤ 40 mg/day (for immediate and extended release)
- Pitavastatin: ≤ 2 mg/day
- Pravastatin: ≤ 40 mg/day
- Simvastatin: ≤ 40 mg/day
- Rosuvastatin: ≤ 20 mg/day
- Other therapies for coexisting conditions require a stable regimen for at least 3 months prior to the Screening and throughout the study including:
 - Standard vitamin supplements
 - Vitamin E (>400 IU)
 - Milk thistle
 - Pentoxifylline

- Diabetic medications:
 - GLP1 agonists and pioglitazone: require a stable regimen for at least 3 months prior to Screening and throughout the study.
 - Insulin: require stable dosing, defined as reasonable dose adjustments (as per Investigator's judgment) to maintain glucose control, for at least 3 months prior to Screening.
 - All other diabetic medications: require a stable dose with reasonable dose adjustment (as per Investigator's judgment) for at least 3 months prior to Screening.
- Antibiotics (not listed in [Appendix 6](#)): Antibiotics for short-term use (<10 days) are allowed; however, chronic, continuous use is not allowed. Use will be at the discretion of the PI.
- Procedural medications (e.g., anti-anxiety medication for MRI scan, anesthetic for liver biopsy) use will be at the discretion of the PI.

7. STUDY TREATMENT DISCONTINUATION AND SUBJECT DISCONTINUATION / WITHDRAWAL FROM THE STUDY

7.1. Discontinuation of Study Treatment for an Individual Subject

Study treatment discontinuation, interruption or dose reduction will be considered if subjects experience the following:

- TEAE of Grade 3 or 4 (per CTCAE V5.0) with severity and relationship noted below
- Any suspected statin-related AE, as determined by the investigator (see below)
- Laboratory result(s) indicative of drug induced liver disease (DILI), based on assessment by the Medical Monitor and by the independent DILI adjudication
- Confirmed diagnosis of HCC
- Progression from Child-Pugh A to Child-Pugh B or C status
- Liver decompensation events
- Subjects with MELD score ≥ 15 .

7.1.1. Specific Actions Taken Will Be As Follows:

- i) TEAE of Grade 3 or 4 (per CTCAE V5.0):
 - Any possibly or probably related Grade 3 TEAE, aldafermin and/or statin may be discontinued or interrupted; evaluation and determination by the PI or the unblinded Medical Monitor in the case of TEAEs possibly related to statin use.
 - Any Grade 4 or higher TEAE, aldafermin and statin will be discontinued
- ii) Any suspected statin-related AE:

Subjects will be allowed a rosuvastatin dose adjustment if the subject experiences a statin-related AE (as determined by the PI). The third-party Medical Monitor will be contacted by the study site to report a possible statin-related AE requiring intervention. Information will be collected on the AE including the specific description, history, and severity based on CTCAE grading. The study team should instruct the subject to refrain from administering the rosuvastatin/placebo therapy and to repeat safety laboratory examinations as indicated by the specific AE within 72 hours. If the subject is <2 weeks from their next visit, they should not dose the rosuvastatin/placebo therapy until the next scheduled visit. If they are >2 weeks from their next study visit, an unscheduled visit should be made to repeat laboratory examinations.

If the AE resolves, subjects will be restarted on a lower dose of over encapsulated rosuvastatin. Subjects on rosuvastatin 20 mg or 40 mg will be restarted on rosuvastatin 10 mg, and subjects on 5 mg or 10 mg will be restarted on rosuvastatin 5 mg. Subjects taking over-encapsulated placebo will be restarted on placebo. In the event that the AE re-occurs upon re-initiation at the lower dose, over encapsulated rosuvastatin/placebo should be discontinued. If the AE does not re-occur with the lower dose, an increase in the over encapsulated rosuvastatin dose may be considered at the subsequent clinic visits according to the protocol algorithm. If the AE re-occurs following administration of this new dose of

rosuvastatin, over encapsulated rosuvastatin/placebo may be reverted to the last tolerated dose. Aldafermin dosing will not be interrupted.

If a subject experiences a statin-related AE of myalgia or rhabdomyolysis (as determined by the PI), information will be collected on the AE including the specific description, history, and severity based on CTCAE grading and forwarded to the designated third-party Medical Monitor who is blinded to treatment assignment but unblinded to laboratory data and statin assignment and dose. The clinical study team will collect a blood sample for safety laboratory evaluations within 48-72 hours. For subjects that have signs or symptoms suggestive of rhabdomyolysis from either muscle symptoms (such as myalgia, pain, weakness, dark urine) or elevated creatine kinase (CK), the origin of the symptoms/CK elevation will be investigated. To this end, the subject will be interviewed about recent heavy exercise, trauma, convulsions, surgery, use of excessive alcohol, morphine, cocaine, or other contributing factors. Additional laboratory tests (creatinine, AST/ALT, total and conjugated bilirubin, potassium, calcium, and/or myoglobin (serum and urine)) will also be performed.

If the subject experienced statin-related increased CK>3 x ULN with clinical symptoms, administration of over-encapsulated rosuvastatin/placebo should be held and may be re-initiated at half the prior dose if follow-up CK is <3 x ULN. If CK rises to >3 x ULN again, the administration of over-encapsulated rosuvastatin/placebo should be held until CK <3 x ULN and can be re-initiated at 5 mg. For subjects experiencing symptoms and CK elevation on 5 mg, over-encapsulated rosuvastatin/placebo should be discontinued.

Aldafermin dosing will continue.

For subjects with suspicion of statin-related myalgia or rhabdomyolysis AND CK 3-5 x ULN, administration of over-encapsulated rosuvastatin/placebo should be held until CK<3 x ULN and may be reinitiated at half the original dose. If symptoms persist and if CK increases >3 x ULN, rosuvastatin should be discontinued. For CK>5 x ULN with clinical suspicion of rhabdomyolysis (ruling out other causes, e.g., recent heavy exercise, trauma, convulsions, surgery, use of excessive alcohol, morphine, cocaine, or other contributing factors), rosuvastatin will be discontinued. Throughout, aldafermin dosing should continue.

iii) Laboratory value(s) suggestive of DILI:

- a) Elevation of AST or ALT >2 x above subject-specific baseline value (calculated using the average of the Day -56 and the Day 1 values) and total bilirubin >1.5 x subject specific baseline value, repeat testing of ALT, AST, and bilirubin must be performed within 48-72 hours. If there are persistent elevations (AST or ALT >2 x baseline or TBL >1.5 x baseline values) upon repeat testing, then close observation (testing and physical examination 2-3 times per week) should be implemented and discontinuation of aldafermin and rosuvastatin should be considered (see below). Note: the unblinded study Medical Monitor will be notified of acute suspected cases and upon identification of suspected DILI cases, the Liver Events Adjudication Committee chair will be notified.
- b) A decision to discontinue or temporarily interrupt the study drug will be considered based on factors that include how much higher than baseline ALT and AST were relative to the ULN and how much the on-study ALT and AST levels have increased

relative to baseline, in addition to whether there is concomitant elevation of bilirubin or INR. aldafermin and rosuvastatin will be discontinued or temporarily interrupted as follows:

- If baseline measurements (BLM) were $<2 \times$ ULN, discontinue if ALT or AST increases to $>5 \times$ BLM
- If BLM $\geq 2 \times$ ULN but $<5 \times$ ULN, discontinue if ALT or AST increases to $>3 \times$ BLM
- Discontinue if ALT or AST increase $>2 \times$ BLM AND the increase is accompanied by a concomitant increase in TBL to $>2 \times$ BLM OR the INR concomitantly increases by >0.2
- Discontinue if total bilirubin $>3.0 \text{ mg/dL}$
- In any subjects with signs and symptoms of fatigue, nausea, vomiting, right upper quadrant pain or tenderness, fever, rash, and/or eosinophilia ($>5\%$).

c) If a subject resides in a remote area, laboratory testing can be performed locally, and the results should be promptly communicated to the investigator site.

d) Close observation for suspected DILI will include:

- Repeating liver enzyme and serum bilirubin tests two or three times weekly. Frequency of repeat testing can decrease to once a week or less if abnormalities stabilize or the study drug has been discontinued and the subject is asymptomatic.
- Obtaining or re-confirming a detailed history of symptoms and prior or concurrent diseases.
- Obtaining or re-confirming the history of concomitant drug use (including nonprescription medications and herbal and dietary supplement preparations), alcohol use, recreational drug use, and special diets.
- Ruling out acute viral hepatitis types A, B, C, D, and E; autoimmune or alcoholic hepatitis; NASH hypoxic/ischemic hepatopathy; and biliary tract disease.
- Obtaining a history of exposure to environmental chemical agents.

Outside of situations listed above, no aldafermin/matched placebo dose reductions will be allowed. Temporary drug holidays from aldafermin dosing <5 days will be allowed on a case-by-case basis for subjects for safety or tolerability but must be approved by the sponsor Medical Monitor or designee. If drug is restarted and is still not tolerated, the subject should stop the medication as multiple drug holidays will not be allowed.

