LDL-C values will be further evaluated at study visit Week 6, 12, 18, 24, 30, 36, and 42, in order to identify subjects who require rosuvastatin initiation or dose-escalation. Specific LDL goal or treatment success criteria are described in detail in [Section 8.3.17](#). Subjects who do not meet rosuvastatin increase criteria will continue on their prior assigned dose of over-encapsulated rosuvastatin/ matched placebo. Subjects on the maximum dose of rosuvastatin 40 mg whose LDL-C levels are still not at goal will continue on the study with rosuvastatin 40 mg unless the subject experiences a cardiovascular-related SAE (e.g., myocardial infarction, CVA). Subjects experiencing a CV-related SAE on rosuvastatin 40 mg will discontinue both aldafermin and rosuvastatin for the remainder of the trial, and cardiovascular care will continue per the subject's regular physician and as per local standard of care practices. Subjects who experience rosuvastatin-related intolerance (by evaluation of muscular symptoms and creatine kinase (CK) levels) will be evaluated by follow-up laboratory testing after the over-encapsulated rosuvastatin/placebo has been held. Depending on the CK levels and clinical status, subjects may be allowed to restart over-encapsulated rosuvastatin/placebo at a reduced dose. Algorithm details are found in [Section 7.1.1](#), part ii.

All subjects will be assessed at Weeks 49 and 54 to confirm their LDL-C levels have decreased to near baseline, at which point no additional follow-up is needed.

Subjects who do not meet LDL-C decrease criteria at Week 54 will have an additional 4-week follow-up visit at Week 58 to confirm that their LDL-C level returned to near baseline. Subjects may remain on statin through Week 58.

As part of safety monitoring, subjects will undergo ultrasound and alpha fetoprotein (AFP) testing at Weeks 24 and 48 to screen for HCC. Subjects with new lesions ≥ 10 mm with AFP > 20 ng/mL will be treated according to local guidelines. If new lesions ≥ 10 mm with AFP > 20 ng/mL occur at Week 24, subjects may continue on study drug at the discretion of the investigator unless or until a clinical diagnosis of HCC is made (defined as LI-RADS 4 or 5 on MRI, or histological confirmation of HCC). For subjects with suspected HCC by ultrasound and AFP screening, additional imaging may be obtained, and data will be gathered for adjudication.

Overall safety will be monitored by a data safety monitoring board (DSMB).

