5.2. Exclusion Criteria

The following will exclude potential subjects from participating the study:

1. Other causes of liver disease that are primary, secondary, or otherwise causes of cirrhosis or which may confound the intended patient population according to the investigator, including but not limited to alcoholic liver disease, hepatitis B, hepatitis C, autoimmune disorders, primary biliary cirrhosis, drug-induced hepatotoxicity, Wilson's disease, hemochromatosis, and alpha-1-anti-trypsin deficiency based on medical history and/or centralized read of liver histology.
2. Evidence of drug induced steatohepatitis secondary to amiodarone, corticosteroids, estrogens, methotrexate, tetracycline, or other medications known to cause hepatic steatosis.
3. History of hepatic decompensation, including variceal bleeding, ascites, or hepatic encephalopathy.
4. Prior or pending liver transplantation.
5. Child Pugh class B and C status.

6. Model of end stage liver disease (MELD) score >12.
7. Evidence of worsening liver disease (defined below) between screening visits (i.e., Day -56 and Day -42) including measures of AST, ALT, alkaline phosphatase (ALP) or total bilirubin (TBL):
 - a. For subjects with TBL, AST, ALT, or ALP baseline levels >ULN, the second assessment should not exceed an increase of 35% over the first assessment.
- Note: An unscheduled visit may be necessary to confirm eligibility if the difference exceeds the allowable percent difference. If performed, unscheduled visit results will be compared to the average of Day -56 and Day -42 results to determine eligibility. If liver function tests are repeated to verify eligibility criteria have been met, there must be a minimum of 14 days (2 weeks) between the Day -42 visit and any unscheduled visit.
8. History of porto-systemic shunt procedure.
9. No evidence of gastroesophageal varices as documented by one of the following assessments:
 - a. A historical and locally evaluated EGD obtained within 365 days of screening or
 - b. A locally evaluated EGD conducted during the screening period

* If no EGD is available, the latest EGD assessment guidelines during a global pandemic† for patients with compensated cirrhosis (i.e., the expanded Baveno VI criteria, [Petta 2018](#)) as follows can be used as a replacement for the EGD to determine eligibility:

 - c. Platelet count >110,000/mm³, and a FibroScan® <30 kPa on a M probe or <25 kPa on a XL probe

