7.2. Discontinuation of Subjects from Study Participation

Subjects will be informed that they are free to withdraw from the study at any time and for any reason. The PI may remove a subject from the study if, in the PI's opinion, it is not in the best interest of the subject to continue the study. Subjects may be discontinued due to a change in compliance with an inclusion/exclusion criterion that is clinically relevant and affects subject safety, occurrence of AEs, occurrence of pregnancy, or administration of non-permitted concomitant medication that might affect subject safety or study assessments/objectives. In addition, for any AEs noted, the PI will determine whether there is impact, or a potential for impact, on subject safety or study assessments/objectives, and will remove such subjects. Subjects will be discontinued due to clinically relevant changes in a subject's status related to Inclusion and Exclusion criteria that significantly affect subject safety or study integrity, development of pregnancy, or necessary administration of non-permitted concomitant medications that might affect subject safety or study assessments/objectives. Notification of discontinuation will be made immediately to the sponsor Medical Monitor or designee. In case of premature discontinuation of study participation, efforts will be made to perform all final EOT and EOS visits/assessments. The date the subject is withdrawn from the study and the reason for discontinuation will be recorded on the subject's Case Report Form (CRF). All withdrawn subjects will be followed until resolution of any AEs or until any unresolved AEs are judged by the PI to have stabilized.

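### The stopping text contradicts itself on confirmed HCC (7.1 against the synopsis, 4.1 and 8.3.19) and, within 7.2, on whether a subject may or must leave the study

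*Protocol*

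**What the plan says.** **Study drug, Section 7.1.** The lead-in is "Study treatment discontinuation, interruption or dose reduction will be considered if subjects experience the following". Seven triggers follow. Four of them are "Confirmed diagnosis of HCC", "Progression from Child-Pugh A to Child-Pugh B or C status", "Liver decompensation events" and "Subjects with MELD score ≥ 15". Section 7.1.1, which sets out specific actions, covers the other three only: Grade 3 or 4 treatment-emergent events, suspected statin-related events, and laboratory values suggesting drug-induced liver injury.

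**Study drug after suspected HCC, synopsis and Sections 4.1 and 8.3.19.** For a new lesion of at least 10 mm with AFP above 20 ng/mL at Week 24, 4.1 says "subjects may continue on study drug at the discretion of the investigator unless or until a clinical diagnosis of HCC is made". The synopsis and 8.3.19 say the same. All three define the diagnosis as LI-RADS 4 or 5 on MRI, or histological confirmation.

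**Study participation, Section 7.2.** One sentence makes discontinuation optional for a clinically relevant, safety-affecting change against an eligibility criterion, for adverse events, for pregnancy, and for non-permitted medication. A later sentence of the same paragraph makes it mandatory for clinically relevant changes "related to Inclusion and Exclusion criteria that significantly affect subject safety or study integrity", for pregnancy, and for necessary non-permitted medication.

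**Entry limits, Section 5.2.** Exclusions include "Model of end stage liver disease (MELD) score >12", Child-Pugh class B or C, any history of decompensation, and any history of HCC.

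**The concern.** HCC and decompensation are among the gravest hepatic events that a trial in compensated cirrhosis can meet. A site that turns to the section headed for treatment discontinuation finds only a duty to consider stopping, with interruption and dose reduction offered as alternatives. A site that turns to the design section or the HCC surveillance section finds that permission to keep dosing lapses at diagnosis. Two subjects with the same diagnosis can then be handled differently because of how the tumour came to light.

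In 7.2 the difficulty is of the same kind, but it concerns leaving the study. A site that reads the first sentence has discretion; a site that reads on has an instruction. The stake is first the safety of the individual subject, and then the consistency with which drug stops and withdrawals are applied across some 80 sites.

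**Working it through.** No sample size, power or error rate depends on this, so the check is a comparison of the text.

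**Step 1: count the actions.** Section 7.1 lists 7 triggers and 7.1.1 gives actions for 3, so 7 − 3 = 4 have none: HCC, Child-Pugh progression, decompensation, and MELD. For those four the discretionary lead-in is the only rule in 7.1. On its own this is missing detail. It becomes a contradiction only where another passage gives a different answer about study drug, and among the four that is HCC.

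**Step 2: follow an HCC diagnosis by route of detection.**

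| How HCC comes to light | Rule on study drug at diagnosis | Source |
|---|---|---|
| Week 24 lesion ≥10 mm with AFP >20 ng/mL | Permission to continue ends | Synopsis, 4.1, 8.3.19 |
| The same subject, read under the trigger list | Stop, interrupt or reduce to be considered | 7.1 |
| Week 24 lesion without a significant AFP change | Local standard of care for the finding; at diagnosis, to be considered | 8.3.19, then 7.1 |
| Week 24 AFP >20 ng/mL without a lesion | Local standard of care for the finding; at diagnosis, to be considered | 8.3.19, then 7.1 |
| Found outside scheduled surveillance | To be considered | 7.1 |

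Rows 1 and 2 give different answers for one subject. Rows 3 to 5 give a different answer from row 1 for the same disease. The wording differs too: 7.1 speaks of a confirmed diagnosis without defining it, while the other passages define a clinical diagnosis.

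**Step 3: how much dosing is in play.** Treatment runs 48 weeks and the on-treatment surveillance visit is Week 24, so a diagnosis made then leaves up to 48 − 24 = 24 weeks of scheduled dosing. The Week 48 surveillance visit coincides with the end of treatment, so little turns on it.

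**Step 4: set the two sentences of 7.2 side by side.**

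| Reason | Optional sentence | Mandatory sentence | Can the two be reconciled as written? |
|---|---|---|---|
| Eligibility change | Clinically relevant and affects safety | Clinically relevant and significantly affects safety or study integrity | Partly, if *significantly* marks a higher tier |
| Pregnancy | Listed without qualifier | Listed without qualifier | No |
| Non-permitted medication that might affect safety or assessments | Listed | Listed, if its use is necessary | Hardly; *necessary* is the only difference |

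Pregnancy is the cleanest case: the same event is optional in one sentence and mandatory in the other.

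**Step 5: entry limits on study.** 7.2 brings eligibility criteria into on-study decisions. Decompensation, Child-Pugh B or C, and raised MELD are exclusions in 5.2 and also triggers in 7.1. The first asks about participation, the second about study drug. The protocol does not say which section a site should apply when such a change occurs, or whether both apply.

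**The case against.** The strongest reply is that the HCC passages can be read together: the specific rule for the Week 24 case governs the general list in 7.1, and it implies a stop rather than ordering one. That is a fair reading for row 1 of the route table. It does not reach rows 3 to 5, where only the general list applies, and it leaves the outcome dependent on the route.

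Second, discretion is not unlimited. Any Grade 4 or higher treatment-emergent event stops both drugs, and total bilirubin above 3.0 mg/dL falls under the stop-or-interrupt rules of 7.1.1. Suspected HCC is adjudicated and the DSMB reviews safety. This stands, and it covers some decompensation events. None of it, by its terms, sets what happens to study drug at an HCC diagnosis.

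Several stronger readings are tempting and are not supported:

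- *Any change in an exclusion criterion removes the subject.* The mandatory sentence in 7.2 is limited by clinical relevance and by a significant effect on safety or integrity, and it sits beside an optional one.
- *7.1 and 7.2 contradict each other outright.* One concerns study drug and the other participation. What is missing is a statement of which governs.
- *The two MELD figures are an error.* An entry limit may properly differ from an on-study trigger. Bilirubin has an entry limit of 1.3 mg/dL and an on-study limit of 3.0 mg/dL. AFP above 20 ng/mL bars entry, yet without a lesion on study it is left to local care. A MELD of 13 or 14 fits that pattern.
- *Week 48 ELF availability will differ by site.* 7.2 asks for efforts to complete the final assessments, ELF is drawn at early withdrawal, an earlier on-treatment value is measured from banked serum, and missing values are multiply imputed. No passage shows a site effect.

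**Conclusion.** The point holds in two places. On HCC, 7.1 leaves study drug to consideration while the synopsis, 4.1 and 8.3.19 end permission to continue at diagnosis on one detection route, so the same diagnosis meets different rules. In 7.2, three overlapping reasons are both optional and mandatory within a single paragraph; pregnancy is irreconcilable as written, and the eligibility reason could be read as two tiers.

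The absence of actions in 7.1.1 for Child-Pugh progression, decompensation and MELD is lack of detail and not a contradiction, but it leaves open whether 7.1 or 7.2 governs.

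The number of subjects affected cannot be derived. A reader might infer one from the introduction's figure of about 45% decompensating over 10 years, but that would count events and not subjects handled inconsistently, and decompensation is not where the study-drug conflict lies. The conclusion rests on reading the HCC passages as ending permission at diagnosis, which is their natural sense although they do not spell out an order to stop. The matter bears on subject safety and should be corrected; it does not affect the validity of the primary analysis.

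**What to change.** Three edits, with the clinical content left to the sponsor and the DSMB:

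1. Reconcile 7.1 and 7.1.1 with the synopsis, 4.1 and 8.3.19 on confirmed HCC, so that one rule applies however the tumour is found and one definition of the diagnosis is used throughout.
2. Reconcile the optional and mandatory sentences of 7.2 for eligibility changes, pregnancy and non-permitted medication. If two tiers are intended for eligibility changes, say what separates them.
3. State whether an on-study departure from an entry limit, such as MELD, Child-Pugh class or decompensation, is governed by 7.1 (study drug), by 7.2 (participation), or by both and in what order. The entry and on-study MELD figures need not be made equal.

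The cost is a few sentences and cross-references in an amendment. No procedure, visit or analysis changes.
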